The primary objectives of this study are to compare the therapeutic impact of liraglutide 368 3 mg versus placebo on reduction of body weight and biochemical hyperandrogenism (as 369 determined by the free androgen index) in obese non-diabetic women with PCOS. We will 1) 370 determine the percentage of participants achieving \geq 5% reduction in baseline body weight with 371 each treatment and 2) assess the inhibition of biochemical hyperandrogenism (ovarian androgen 372 production and sex hormone binding capacity) in response to each treatment.

373 Secondary study objectives

The secondary study objectives are to determine the effect of treatment with antiobesity medication versus placebo on anthropometric, **clinical**, hormonal and metabolic parameters in non-diabetic obese women with hyperandrogenism.

377

378 EFFICACY VARIABLES/MEASURES

379 *Primary endpoints*

The co-primary end points are to compare obese women with PCOS receiving liraglutide 3mg (LIRA 3 mg) with those receiving placebo on body weight and bioavailable ovarian androgen

- 382 concentrations as determined by:
- 1a. percent change in body weight from baseline to week 30 and
- 1b percentage of participants achieving ≥5% reduction in body weight from baseline
 to week 30
- 3862reduction of free androgen index [FAI=testosterone (T)/sex hormone binding387globulin (SHBG) levels] from baseline to 30 weeks
- 388 Secondary endpoints
- 389 We will further examine the impact of the administration of these pharmacotherapies in obese
- 390 non-diabetic PCOS women on:
- 391 Anthropometric and Clinical Indices
- Change from baseline of body mass index [BMI], absolute body weight, waist circumference (WC), waist: hip ratio (WHR), waist-height ratio (WHtR), and whole-body dual-energy X-ray absorptiometry [DXA]) measures of body composition (trunk fat mass and truck fat/extremities fat ratio) to determine the relative contribution of changes in fat mass (FM) vs. lean mass (LM) to overall weight loss at week 30
- 2. Compare women with hyperandrogenism for frequency of patients achieving a body
 weight reduction of at least 10% [Time Frame from baseline to 30 weeks]
- 399 3. Change in menstruation frequency (normalized to the number of menstruations per year) from before and after 30 weeks of treatment
- 401 Metabolic Parameters
- 402 1. Change in glycemic values from baseline to 30weeks
- 403 2. Fasting and 2 hour glucose levels after an OGTT

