729 Several other endpoints will be assessed at each study visit. Baseline blood samples will 730 also be collected for measurement of lipid profiles (cholesterol, HDL and LDL cholesterol, and triglycerides), adrenal androgens (DHEAS), and liver enzymes (AST/ALT). Dyslipidemia is defined
as the presence of at least one of the mentioned lipid parameters abnormalities.

733 Safety assessments

The safety and tolerability assessments will include incidence and intensity of adverse events, withdrawals because of adverse events, physical exams, vital sign measurements and clinical laboratory parameters. Patients will be seen at 16-18 weeks and 30-32 weeks for laboratory evaluation for a complete chemistry profile and to confirm they are not pregnant. Patients will also be required to perform monthly home pregnancy tests.

739 STATISTICAL/ANALYTICAL PLAN

740 Statistical Methods

Statistical analysis will be performed using SPSS version 15.1 for Windows (SPSS, Inc.; 741 742 Chicago, IL). Continuous variables will be tested for normality of distribution using the Kolmogorov-Smirov test. When necessary, non-normally distributed data will be subjected to 743 logarithmic or square-root transformation to obtain a normal distribution where necessary for 744 subsequent analyses. The primary endpoints are comparison of percent change in body weight 745 and therapeutic impact on biochemical hyperandrogenism (as determined by FAI) from baseline 746 747 to week 30 of treatment. The secondary endpoints include changes in surrogate measures of insulin action (HOMA-IR, SI_{OGTT}, IGI/HOMA-IR and IS-SI) and glycemic parameters (fasting blood 748 glucose [FBG] and 2 hour post OGTT glucose), glucose and insulin AUC, and mean blood glucose 749 (MBG), anthropometric parameters (BMI, absolute weight, WC and fat distribution by DXA), 750 751 blood pressure, lipid profiles, and adrenal androgen levels (DHEAS). Direct and indirect estimates of insulin sensitivity and secretion (HOMA, SI_{OGTT}, IGI/HOMA, β-cell compensatory 752 753 function, glycemic parameters (FBG, MBG, 2 hour post OGTT glucose level, AUC) anthropometric 754 measurements (body weight, BMI), fat distribution (WC, WHR and WHtR), BP, androgen and 755 lipid profiles will be considered as dependent variables.

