For all analyses, in which the measures are continuous, data from evaluable subjects will be submitted to a repeated-measures general linear model (SS/ Drug treatments x repeated measures ANOVA) including the arm of drug treatment (liraglutide 3mg vs. placebo) as the between-subjects effect, and the visit (baseline and 30 wks) as the within-subjects effect. To evaluate the differences in the response to each treatment over visits, the interaction effect will be calculated. Baseline comparisons between groups will be made by one-way ANOVAs.

Frequency of patients achieving a body weight reduction of at least 5% and 10% before and after treatment will be compared with the McNemar test (complex chi square $[\chi^2]$ for paired data), which formally tests for a change between the observed proportions of k related samples. Dysglycemia occurrence before and after different treatment will also be compared with the McNemar test. The difference in frequency of menstruation before and aftertreatment will also be compared using the McNemar test.

Data will be analyzed on completed treatment parameters where relevant (evaluable population). The evaluable population is defined as all randomized subjects who complete treatment through week 30-32 week. Results will be reported as mean +/- S.E.M for normally distributed data and as median (interquartile range) if the distribution is not normal. Categorical data will be presented as percentage. P < 0.05 is considered statistically significant.

773

774 Sample Size and Justification

775 A priori sample size analysis was performed using the online calculator provided by the 776 Hospital Mallinckrodt General Clinical Massachusetts General Research Center (http://hedwig.mgh.harvard.edu/sample size/size.html). To calculate sample size, we used the 777 778 standard formula suggested for clinical trials by considering a type one error (α) of 0.05 and type 779 two error (β) of 0.20 (power = 80%). Sample size calculation revealed that 57 participants 780 randomized in a 2:1 ratio (liraglutide: placebo) were needed. Using a 30% drop-out rate, the 781 study is designed to recruit 92 patients, enroll 48 liraglutide and 24 placebo to ensure that the 782 number of subjects completing the study (38 LIRA/19 PL) as derived by the sample size 783 calculation is met.

784

785 Ethical and Regulatory Requirements

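### The co-primary ≥5% weight-loss responder endpoint is tested before versus after treatment with McNemar, which does not compare liraglutide with placebo

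*Combined protocol and SAP*

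**What the plan says.** **The endpoint.** Under Primary endpoints, the plan writes "The co-primary end points are to compare obese women with PCOS receiving liraglutide" 3 mg with those receiving placebo. It then lists percent weight change (1a), "1b percentage of participants achieving ≥5% reduction in body weight from baseline" to week 30, and reduction of the free androgen index, FAI (2).

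**The test.** Statistical Methods says that "Frequency of patients achieving a body weight reduction of at least 5% and 10% before and after treatment" will be compared with McNemar's test for paired data. The same test is named for dysglycemia and for menstrual frequency. For continuous measures the plan has a repeated-measures model with arm and visit, in which "the interaction effect will be calculated"; that is a comparison of the arms. No such comparison is given for any proportion.

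**The primary list.** The opening sentence of the Primary objective covers "placebo on reduction of body weight and biochemical hyperandrogenism". Its first numbered aim is to "determine the percentage of participants achieving" a loss of at least 5%, and it numbers no other weight measure. Statistical Methods says "The primary endpoints are comparison of percent change in body weight" and impact on FAI. It puts the 5% responder measure in neither its primary nor its secondary list.

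**The decision rule.** The only rule is "P < 0.05 is considered statistically significant". The plan does not say whether one primary or all of them must be met.

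**The concern.** Endpoint 1b exists to compare two arms, but the named test sets the same women before treatment against themselves after it. Responder status is defined by change from baseline, so the before proportion is zero by construction. The test then asks only whether some women lost 5%. All participants receive diet and lifestyle counselling, so some responders are likely in both arms even if the drug adds nothing.

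A report that follows the plan could present a small p-value for a co-primary endpoint that carries no information about liraglutide against placebo. If the test is run within each arm, the 2:1 allocation alone makes significance easier to reach on liraglutide.

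The second, lesser matter is that a reader cannot tell from the text whether 1b counts towards the primary claim, or what combination of results makes the trial positive.

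**Working it through.** **Inputs.** From Sample Size and Justification: 38 liraglutide and 19 placebo completers, α = 0.05 (sidedness not stated; two-sided taken here). The total of 57 cannot be reproduced, because the plan names no effect size, SD, response rate or endpoint for it. It is used here only as the arm sizes. All response rates and correlations below are assumptions.

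**1. McNemar with an empty cell.** Let b be the number of women who are non-responders before and responders after, and c the reverse. Nobody is a responder at baseline, so c = 0 and b is the responder count.

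- Exact: p = 2 × 0.5^b
- Uncorrected: χ² = (b − c)²/(b + c) = b
- Continuity-corrected: χ² = (b − 1)²/b

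| Version | Just misses 0.05 | First below 0.05 |
|---|---|---|
| Exact | b = 5, p = 0.0625 | b = 6, p = 0.031 |
| Corrected | b = 5, p = 0.074 | b = 6, p = 0.041 |
| Uncorrected | b = 3, p = 0.083 | b = 4, p = 0.046 |

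Neither the arm size nor the other arm's result enters any formula.

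**2. Run per arm (assumption): an example with equal arms.** Take 8/38 = 21% and 4/19 = 21%.

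- Liraglutide, exact: 2 × 0.5^8 = 0.008
- Placebo, exact: 2 × 0.5^4 = 0.125
- Fisher's exact test between arms: p = 1.00

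With the uncorrected version, the placebo arm would also pass here (p = 0.046). The contrast depends on the version, so both thresholds are carried forward.

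**3. Run per arm: chance that only the larger arm is significant when the true rate r is the same.** P[Bin(38, r) ≥ k] × P[Bin(19, r) < k]:

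| r | k = 6 | k = 4 |
|---|---|---|
| 0.10 | 0.173 | 0.474 |
| 0.15 | 0.487 | 0.576 |
| 0.20 | 0.669 | 0.437 |
| 0.25 | 0.627 | 0.261 |
| 0.30 | 0.467 | 0.133 |
| 0.40 | 0.163 | 0.023 |
| 0.50 | 0.032 | 0.002 |

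For example, at r = 0.20 and k = 6: 0.7996 × (1 − 0.1631) = 0.669. At high rates the chance falls because both arms then pass.

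**4. Run pooled.** With r = 0.20 in both arms, P[Bin(57, 0.20) ≥ 6] = 0.981.

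**5. Primary list and success rule.** Percent weight change and FAI, both at 0.05, with no true effect on either:

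- Either suffices: if independent, 1 − 0.95² = 0.0975. Simulation at 38/19 (t-tests on the changes, 40,000 replicates per setting, correlation 0 to 0.7) gave 0.082 to 0.098.
- Both required: error is at or below 0.05. Joint power is below that of each endpoint; for example, 0.80² = 0.64 if each has an assumed 80% and they are independent.

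**The case against.** **A between-arm comparison is implied.** The endpoint section does state that purpose. But Statistical Methods gives an arm comparison only for continuous measures, and names a specific different test for proportions. An analyst who follows the text would run McNemar. This objection does not rescue the test.

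**The arm-size artefact is not in the plan.** This stands in part. The plan does not say that McNemar is run within each arm. A reader might infer that it carries a false-positive rate of 17–67%; the documents do not support that. The range belongs to one reading and to assumed rates. Under pooling there is no arm-size artefact, and the test is simply uninformative about treatment. The defect needs neither figure.

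**The sections do not really disagree on the weight primary.** This largely stands. A reader might infer that they conflict over which weight measure is primary. In fact percent change and FAI are primary in both the endpoint list and Statistical Methods. The open question is only whether 1b is primary too. It is not cosmetic, because 1b is the only weight measure in the numbered objectives.

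**Error is not inflated.** A reader might infer from the single 0.05 threshold that the trial's error exceeds 5%. The documents lean the other way. Co-primary usually means that all are required, and the Study Hypothesis describes a fall in androgens brought about by weight loss, which needs both to move. The 8–10% applies only if either endpoint suffices and neither is affected. What remains is an unstated rule.

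**The interaction test already covers weight.** It fits absolute weight at two visits. Percent change is one value per woman with no baseline counterpart, so the model does not match 1a exactly; the calculation in step 5 uses a t-test on percent change instead.

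**Conclusion.** The responder test is wrong as written. A listed co-primary endpoint meant to compare liraglutide with placebo has only a before/after test, whose result is fixed by the responder count: significance from 6 responders (exact or corrected) or 4 (uncorrected), irrespective of the other arm. This follows from the definitions and needs no assumption.

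The size of the consequence does need assumptions. Per arm, with equal true rates of 10–30%, only the larger arm is significant 17–67% of the time at threshold 6, or 13–58% at threshold 4, falling to 3% and 0.2% at a 50% rate. Pooled, at 20% in both arms, the exact test is significant about 98% of the time.

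The status of 1b and the missing success rule call for clarification; they do not show that error is inflated. Percent change and FAI are consistently primary. If both are required, error is controlled; if either sufficed it would be about 8–10%.

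**What to change.** 1. In Statistical Methods, replace McNemar for the ≥5% and ≥10% responders with a comparison of the two proportions between arms, for example Fisher's exact test. The cost is that P < 0.05 is reached less easily than with McNemar.
2. Use the same primary list in Primary objective, Primary endpoints and Statistical Methods, and say explicitly whether 1b is on it. The sponsor may keep it as primary or make it key secondary.
3. State one success rule. Either all co-primaries are required at 0.05 each, which fits the label, or the endpoints are tested in a fixed sequence. Under the first, joint power is lower than for each endpoint, and lower still if 1b stays on the list. Under the second, a later endpoint cannot be claimed once an earlier one fails.

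This is a few lines in three sections, with no added patients, visits or data.

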- Surrogate measures of insulin action derived from 75 gram OGTT [insulin sensitivity index (HOMA-IR, Matsuda index), corrected early insulin secretory response (insulinogenic index/HOMA-IR), area under the curve (AUC) for insulin and glucose, and oral disposition index (product of Matsuda index and insulinogenic index; SI_{OGTT} x Δinsulin 30–0 min to
- 408 glucose 30–0 min)]

- 409 Cardiovascular Risk Factors (change from baseline to 30 weeks)
- 410 1. Plasma lipid fractions
- 411 2. Blood pressure
- 412 Other endocrine levels (change from baseline to 30 weeks)
- 413 1. Adrenal androgen concentration- dehydroepiandrosterone sulfate (DHEAS) levels
- The following will be documented for each patient:
- Presence of polycystic ovary syndrome (PCOS) will be recorded using modified National Institutes of Health (NIH) criteria which are inclusive of presence of oligo-/amenorrhea (cycle >35 days or <8 cycles year), and clinical and/or biochemical hyperandrogenism, after exclusion of related disorders. Other causes to bleeding irregularities and androgen excess will be excluded.
- 2. Metabolic syndrome (MetS) will also be documented and defined (2005 National Cholesterol Education Program, Adult Treatment Panel III) as the presence of at least three of the following criteria: abdominal obesity (waist circumference >80 cm in women); serum triglycerides ≥1.7 mmol/L; serum HDL <1.3 mmol/L; systolic blood pressure ≥130 mmHg and/or diastolic blood pressure ≥85 mmHg; and fasting plasma glucose ≥7.0 mmol/L
- 426

427 Safety variables/Measures

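### A single P < 0.05 rule covers about 26 secondary tests with no multiplicity rule or exploratory label, so the chance of at least one false-positive secondary is many times 5%

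*Combined protocol and SAP*

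**What the plan says.** The Statistical Methods section ends with one decision rule: "P < 0.05 is considered statistically significant". Nothing limits it to the primaries. The sample size section uses the same level, "considering a type one error (α) of 0.05", without naming the endpoint it applies to or saying whether the test is one- or two-sided.

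The secondaries are listed twice. The Secondary endpoints section groups them as anthropometric and clinical, metabolic, cardiovascular and other endocrine measures. Statistical Methods gives an overlapping list that opens "The secondary endpoints include changes in surrogate measures of" and runs through insulin action, glycemia, body size, blood pressure, lipids and DHEAS.

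Each continuous measure gets a repeated-measures model with a treatment-by-visit interaction. Weight response at 5% and 10%, dysglycemia and menstrual frequency are assigned to the McNemar test. Results are to be shown as mean with standard error, or as median with interquartile range. The documents contain no multiplicity adjustment, testing order, alpha split, exploratory label or planned confidence interval.

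**The concern.** The plan separates primary from secondary endpoints by name but not by what may be concluded from each. A secondary result below 0.05 has the same status as a primary one. With no planned confidence intervals, the comparison with 0.05 is the only inferential statement prescribed for each secondary.

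This matters because the Study Hypothesis section expects weight loss to improve hormonal and cardiometabolic parameters, and most of those are secondary endpoints. In a trial planned around 57 completers, a few chance findings among many tests could not be told apart, under the plan's own rule, from real effects. Overlapping measures make this worse. BMI and absolute weight largely restate percent weight change, and mean glucose and glucose AUC come from the same OGTT values. A cluster of significant results could look like independent confirmation when it is one signal counted several times.

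**Working it through.** The plan states no family-wise error rate, so there is no figure of its own to reproduce here. The inputs taken from it are the 0.05 threshold (Statistical Methods) and the planned completers, 38 liraglutide and 19 placebo (Sample Size and Justification). Two-sided testing is assumed, which puts 0.025 in the direction of benefit.

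**Step 1: count the secondary tests** (Secondary endpoints and Statistical Methods sections).

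| Group | Tests |
|---|---|
| BMI, absolute weight, waist, waist:hip, waist:height | 5 |
| DXA trunk fat, trunk/extremity fat ratio | 2 |
| 10% weight response | 1 |
| Menstrual frequency | 1 |
| Fasting, 2-hour and mean glucose | 3 |
| HOMA-IR, Matsuda, IGI/HOMA-IR, IS-SI | 4 |
| Glucose AUC, insulin AUC | 2 |
| Lipids | 4 |
| Systolic and diastolic pressure | 2 |
| DHEAS | 1 |
| Dysglycemia | 1 |
| **Total** | **26** |

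Other reasonable counts run from 24 to 31. Leaving out dysglycemia and adding DXA fat mass and lean mass gives 26 − 1 + 2 = 27. Adding dysglycemia back, with testosterone, SHBG and the fat distribution index, gives 27 + 4 = 31.

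**Step 2: independent tests, no true effects, either direction.**
- Expected false positives: 26 × 0.05 = 1.3.
- At least one: 1 − 0.95^26 = 1 − 0.264 = 0.736, or 74%.
- Across the counts: 71% for 24 and 80% for 31.

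Three of the 26 (10% response, dysglycemia, menses) are McNemar before/after tests, and their false-positive rate for a drug effect is not fixed at 5%. Without them, 1 − 0.95^23 = 1 − 0.307 = 0.693, or 69%.

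**Step 3: correlated tests.** The documents give no correlations, so these are assumed. For each setting 10,000 trials of 38 versus 19 were simulated with no true effects, using a two-sample t test per endpoint. With two visits, the planned interaction test is equivalent to a t test on change. Every endpoint was treated as continuous, which is a simplification for the binary ones.

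| Assumed correlation | 27 endpoints, either direction | 27 endpoints, benefit | 16 endpoints, either direction | 16 endpoints, benefit |
|---|---|---|---|---|
| 0.3 throughout | 64% | 34% | 47% | 25% |
| 0.5 throughout | 49% | 26% | 38% | 19% |
| 0.7 throughout | 32% | 16% | 27% | 13% |
| 0.5–0.9 within domains, 0.1–0.3 between | 42–65% | 21–36% | 33–49% | 17–27% |

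A uniform correlation of 0.9 across all measures, an extreme case, gives 17% in either direction for 27 endpoints and 7.6% for benefit on 16.

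**Step 4: false benefit on metabolic, cardiovascular or hormonal endpoints only.** The 16 are five glycemic and AUC measures, four insulin-action indices, four lipids, two blood pressures and DHEAS. Dysglycemia, testosterone and SHBG would make 19. If independent, 1 − 0.975^16 = 33% and 1 − 0.975^19 = 38%. With the assumed correlations above, 16 endpoints give 13% to 27%. A single two-sided test allows 2.5% in that direction, so even 13% is about five times as much.

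**The case against.** A reader might infer that a false metabolic or hormonal benefit is likely, meaning more probable than not. The documents do not support that. The 74% needs all 26 tests, either direction and independence. Independence is contradicted by the plan's own definitions: the insulin indices, AUCs and mean glucose all come from one OGTT, and BMI comes from weight. Limited to favourable findings on the relevant endpoints, the figure stays below one half even under independence.

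A reader might also infer that chance findings will be presented as established benefit. Nothing in the documents says so; the plan leaves that open without intending it.

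It can be said that the secondary label already signals lower standing, and that unadjusted secondaries do not affect the primary result. The second part is true and limits the seriousness. The first is weaker, because the only stated rule makes no distinction between the tiers.

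It can also be said that the drug probably affects some of these measures, so a null across all of them is unrealistic. The risk then remains for the unaffected ones. If 10 of the 26 were truly null (an assumption) and independent, it would be 1 − 0.95^10 = 40% in either direction, or 1 − 0.975^10 = 22% for benefit.

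The McNemar point stands. Both arms receive lifestyle counselling, so a before/after change can occur without any drug effect, and the error rate of those three tests could exceed 5%. That is a separate problem of test choice.

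**Conclusion.** The concern holds as a gap in error control and labelling. One unrestricted 0.05 rule covers about 26 secondary tests, and nothing in the plan limits or qualifies what may be claimed from them. With no true effects, the chance of at least one false-positive secondary is 74% if the tests are independent, and roughly 30% to 65% under assumed moderate to strong correlation. The narrower risk of a false metabolic, cardiovascular or hormonal benefit is about 33% to 38% if independent, and about 13% to 27% for 16 correlated endpoints. That is real but not more likely than not.

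These figures rest on two-sided testing, assumed correlations, no true effect on the endpoints counted, and treating the McNemar outcomes as ordinary 5% tests, which they are not. The primary analysis is unaffected. The plan should be changed because the remedy is cheap and alters what the trial can legitimately conclude.

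**What to change.** Replace the significance sentence in Statistical Methods with: *Statistical significance at P < 0.05 is claimed only for the primary endpoints; secondary endpoints are reported as between-arm estimates with 95% CIs and nominal p-values, unadjusted for multiplicity and labelled exploratory.*

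Keep BMI and absolute weight as listed endpoints, with a note that they largely restate percent weight change. For 10% response, dysglycemia and menses, the new sentence calls for an arm difference that the McNemar test does not supply, so those lines need to be brought into agreement with it. The sentence does not settle how the primary endpoints combine. The endpoint section lists three and Statistical Methods two, with no combining rule, and that needs its own statement.

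The cost is that fewer secondary results can be called significant. No extra patients, visits or assays are needed. It is a protocol revision, so it requires advance written IRB approval under the Safety variables/Measures and Ethical and Regulatory Requirements sections.

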Up to 92 non-diabetic women with PCOS, aged 18 years to 45 years of age, meeting BMI 451 criteria, will be invited to participate. We will define hyperandrogenism using biochemical 452 453 evidence (elevated testosterone and/or free androgen index with exclusion of androgen secreting tumors). Subjects will be recruited using flyers distributed in the metabolic clinic, 454 455 gynecology clinics and pathology laboratory associated with Woman's Hospital. All participants will be provided a written informed consent and be asked to sign a copy before being enrolled in 456 457 the study. The Woman's Hospital Institutional Review Board (WHIRB) will have approved both the protocol and consent. All subjects will undergo a verbal screen, and if they are eligible and 458 459 sign a medical release form, their medical records will be obtained to confirm their medical history. All subjects will provide a medical and gynecological history including assessment of 460 regularity and length of the menstrual cycle, with recording of menses in the 12-month period 461 before the study. Patients will be specifically asked about the number of menses in previous 12 462 463 months (menstrual frequency). To be eligible for the study, subjects will be required to have 464 irregular periods (cycle length outside 24–35 days or <8 cycles per year). All enrolled patients will then undergo baseline clinical and laboratory evaluations to exclude diabetes, thyroid 465 466 disorder, significant hyperprolactinemia, elevated liver enzymes and/or severe hypertriglycidemia. A negative serum pregnancy test is a prerequisite for commencing 467 468 treatment. Subjects will be instructed to use an IUD or double barrier methods of contraception (unless sterilized) during the study since hormonal methods are not permitted. Glycemic status 469 470 will be measured at the beginning and end of each treatment period by a standard 75g oral 471 glucose tolerance test (OGTT). Obese women who meet study eligibility criteria (see inclusion and exclusion criteria) will be eligible to be randomized to treatment. We anticipate that 72 472 473 women will be randomized to treatment (this allows for 20 women to fail screening). Exclusion 474 criteria include any condition, which in the opinion of the investigator would place the subject at 475 increased risk or otherwise make the subject unsuitable for participation in the study.

- 476 Key Inclusion Criteria
- 477 Female gender
- 478 18-45 years of age

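### A 30% drop-out from 72 randomised women leaves about 50 completers, not the 57 that the sample size calculation requires

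*Combined protocol and SAP*

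**What the plan says.** Sample Size and Justification sets the type I error at 0.05 and the type II error at 0.20. It then reports the result: "Sample size calculation revealed that 57 participants", allocated 2:1, were needed. The allowance for losses follows: "Using a 30% drop-out rate", the "study is designed to recruit 92 patients, enroll 48 liraglutide and 24 placebo to ensure that the" "number of subjects completing the study (38 LIRA/19 PL) as derived by the sample size" calculation is met. So 57 (38 + 19) is the number who must complete, and 72 (48 + 24) is the number randomised.

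The Subjects section (under Study Plans and Procedures) explains the step from 92 to 72: it anticipates that 72 "women will be randomized to treatment (this allows for 20 women to fail screening"). The Study Hypothesis section also gives 72 women at 2:1.

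Statistical Methods defines the evaluable population as randomised women who complete treatment through the final visit window, and analyses the continuous measures in evaluable subjects.

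**The concern.** The drop-out rate, the number randomised and the number completing are linked by one multiplication, and the three stated values do not satisfy it. The 30% allowance is there to protect the 57 completers, and 72 randomised does not do that.

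This is the plan's only justification of its size. Because efficacy is analysed in completers, every woman lost is lost to the primary comparison. At the stated drop-out rate, the trial would analyse fewer women than its own calculation requires. A non-significant result would then be read against 80% power when the plan's own figures imply less.

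**Working it through.** **Inputs.** From Sample Size and Justification: 57 completers (38/19), 30% drop-out, 72 randomised (48/24), 92 recruited, α = 0.05, power 80%. From Subjects: 92 − 72 = 20 screen failures. The plan states no effect size, SD, response rates, endpoint or sidedness for the calculation, so the 57 cannot be reproduced. It is taken as given below.

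**1. Can the 72 be reproduced from 57 and 30%?**

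- Required number randomised = completers/(1 − drop-out) = 57/0.70 = 81.4, so 82.
- By arm: 38/0.70 = 54.3, so 55; 19/0.70 = 27.1, so 28; total 83. An exact 2:1 split gives 56/28 = 84.
- The 72 is not reproduced. It falls 10 to 12 short.

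**2. What does 30% drop-out leave from 72?**

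- 72 × 0.70 = 50.4 in total; 48 × 0.70 = 33.6 on liraglutide; 24 × 0.70 = 16.8 on placebo.
- Shortfall: 57 − 50.4 = 6.6 women.

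**3. What drop-out fits 72 and 57?**

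- (72 − 57)/72 = 15/72 = 20.8%. Working forwards with 20%: 57/0.80 = 71.25, so 72.

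**4. Does another reading of the 30% work?**

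| Reading | Result | Fits 30%, 72 and 57? |
|---|---|---|
| Loss from 92 to 57 | 1 − 57/92 = 38.0% | No |
| Loss from 92 to 72 | 1 − 72/92 = 21.7%, and assigned to screening | No |
| 30% taken off 92 | 92 × 0.70 = 64.4 | No |
| Multiply 57 up by 1.3 | 57 × 1.3 = 74.1, so 75 | No |

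The last is the closest, but it is an incorrect way to inflate for drop-out, and 72 randomised with 30% loss still leaves about 50.

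**5. Effect on power.** Assume a two-sided two-sample t-test at 0.05 and accept the plan's premise that 38/19 gives 80%. Solving the noncentral t distribution, with noncentrality d/√(1/n₁ + 1/n₂) and n₁ + n₂ − 2 degrees of freedom, gives a standardised difference d = 0.80.

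| Completers | Power at d = 0.80 | Difference detectable with 80% power |
|---|---|---|
| 38/19 | 80.0% | 0.80 SD |
| 34/17 | 75.3% | 0.85 SD |
| 33/17 | 74.9% | 0.85 SD |

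Other methods agree. At the fractional sizes 33.6/16.8, the normal approximation (d = 0.787) gives 75.0%, and a one-sided test re-solved for 80% at 38/19 gives 75.6%. A two-proportion test gives 73.7% to 74.7% over assumed placebo response rates of 5% to 30%.

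**6. Chance of reaching the target.** If each woman drops out independently with probability 0.30, the chance that at least 57 of 72 complete is P(Binomial(72, 0.70) ≥ 57) = 5.5%.

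**The case against.** The arithmetic cannot be disputed, but its weight can be. First, the plan gives no effect size, so true power at either 57 or 50 completers is unknown. The word *ensure* in the plan governs the number of completers, and 80% is an input to the calculation. Second, the demonstrated loss is about 5 percentage points of power. It arises only if drop-out reaches 30%; at about 21%, 72 women do yield 57. Third, the error affects neither the treatment estimate nor the type I error. Fourth, the Discontinuations section calls for the final evaluation when a woman leaves the study, so some drop-outs may have outcome data.

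The first two points stand as limits: the power figure is conditional on the plan's premise, and the loss is moderate. The third is true but does not make the stated figures consistent. The fourth does not help, because the efficacy analysis is confined to women who complete treatment. None of these reconciles 30%, 72 and 57. The missing effect size, SD and endpoint are a separate reporting gap, and the conclusion here does not depend on them.

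**Conclusion.** The concern holds. On the plan's own figures, 30% drop-out from 72 randomised leaves about 50 completers, and the assurance of 38/19 is wrong as written. That step needs no assumption beyond the numbers stated.

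The size in power terms rests on two assumptions: that 57 completers at 38/19 do give 80%, as the plan says, and that the comparison behaves like a two-sided two-sample t-test. Power then falls to about 75%, with the detectable difference rising by about 0.05 SD. The completer target would be missed about 19 times in 20 under independent 30% drop-out. The shortfall is moderate, but it lies in a figure that readers will rely on.

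**What to change.** Make the three figures in Sample Size and Justification agree. Either of two corrections needs no extra enrolment:

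- State that 72 randomised gives 57 completers at a drop-out of about 20%, and give the reason for expecting that rate. The documents offer none at present.
- Keep 30%, and state about 50 completers (34/17 or 33/17) with about 75% power for the planning effect.

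Both cost protocol wording only, though the stated drop-out allowance or power becomes less favourable. If the sponsor wants to keep both 30% and 80%, the number randomised has to rise to 82 to 84, which is 10 to 12 more women, with recruitment above 92 to match if the allowance for 20 screen failures is kept.

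In the same edit, it would help to state the endpoint, difference and SD (or response rates) behind the 57, and the resulting power for percent weight change, the ≥5% responder rate and the free androgen index. Only the sponsor can supply these inputs.
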